7.6. Concomitant Therapy

Any medication or vaccine (including over-the-counter or prescription medicines, vitamins, and/or herbal supplements) that the participant is receiving at the time of enrollment or receives during the study must be recorded along with:

- reason for use
- dates of administration including start and end dates
- dosage information including dose and frequency

Concomitant therapy with another biological therapy (e.g., monoclonal antibodies or IV immunoglobulin therapy) should be discussed with the GSK Medical Monitor prior to beginning therapy. If allowed, therapy should not be administered at the same time as the mepolizumab injection(s) and physicians should take measures to separate administration of another biological therapy as long as possible from administration of mepolizumab.

The GSK Medical Monitor should be contacted if there are any questions regarding concomitant or prior therapy.

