9.1.2. Change in mean daily OCS dose from Weeks 0-4 to Weeks 16-20

9.1.2.1. Endpoint / Variables

The mean daily OCS (prednisone or equivalent) dose for each 4 week period (Week 0-4, Week 4-8, Week 8-12, Week 12-16 and Week 16-20) for each subject will be calculated as the sum of the daily doses of OCS during each period divided by the total number of days, 28. For each subject, the prednisone equivalent daily dose for each day will be determined as described in Section 13.4.4.

Subjects withdrawing from the study prematurely will have mean daily OCS (prednisone or equivalent) dose calculated using available data up to study withdrawal date only (divided by the number of days for which there is available data).

The change in the mean daily OCS dose from Week 0-4 to Week 16-20 will be calculated for each subject as the mean daily OCS dose for Week 16-20 minus the mean daily OCS dose for Week 0-4. The change in the mean daily OCS dose from Week 0-4 to each 4-week period (Week 4-8, Week 8-12 and Week 12-16) will be calculated using the same formula. The change in mean daily OCS dose will be summarised separately for a) all subjects and b) for subjects with a mean Week 0-4 OCS dose > 0mg.

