13.3.2. Reporting Standards

General	

 All data displays (Tables, Figures & Listings) will use the term “Subject” rather than “Participant” which reflects CDISC and GSK Data Display Standards terminology. The current GSK Integrated Data Standards Library (IDSL) will be applied for reporting, unless otherwise stated (IDSL Standards Location: https://spope.gsk.com/sites/IDSLLibrary/SitePages/Home.aspx): 
 4.03 to 4.23: General Principles 5.01 to 5.08: Principles Related to Data Listings 6.01 to 6.11: Principles Related to Summary Tables 7.01 to 7.13: Principles Related to Graphics Do not include subject level listings in the main body of the GSK Clinical Study Report. All subject level listings should be located in the modular appendices as ICH or non-ICH listings 	
Formats	

 GSK IDSL Statistical Principles (5.03 & 6.06.3) for decimal places (DPs) will be adopted for reporting of data based on the raw data collected but may be adjusted to a clinically interpretable number of DPs. 	
Planned and Actual Time	

 Reporting for tables, figures and formal statistical analyses: 
 Planned time relative to dosing will be used in figures, summaries, statistical analyses and calculation of any derived parameters, unless otherwise stated. The impact of any major deviation from the planned assessment times and/or scheduled visit days on the analyses and interpretation of the results will be assessed as appropriate. Reporting for Data Listings: 
 Planned and actual time relative to study drug dosing will be shown in listings (Refer to IDSL Statistical Principle 5.05.1). 	

 • Unscheduled or unplanned readings will be presented within the subject’s listings. • Visits outside the protocol defined time-windows (i.e. recorded as protocol deviations) will be included in listings, summaries and statistical analyses. 	
Unscheduled Visits	

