The definition of HES flare for this study (205203) is different from that for the preceding, randomized Study 200622. This difference in definitions is due to the requirement during Study 200622 to avoid decreases in background HES therapy that may confound a blinded subject’s clinical status as well as the requirement in Study 200622 to blind blood eosinophil levels. In Study 205203, all participants will receive mepolizumab and investigators will be unblinded to blood eosinophil levels starting 4 weeks after the first dose (Visit 2) so that they may adjust background HES therapy as per SoC.

Rate of HES Flares

- For subjects completing the study, the rate of HES flares will be calculated as

$$\frac{365.25 \times \text{Number of observed HES flares}}{\text{Date of Week 20 (Visit 6)} - \text{Date of first dose of mepolizumab} + 1}$$
- For subjects withdrawing prematurely from the study, the rate of HES flares will be calculated as

$$\frac{365.25 \times \text{Number of observed HES flares}}{\text{Date of study withdrawal} - \text{Date of first dose of mepolizumab} + 1}$$

The number of HES flares is the number of unique starting dates for HES flares. To be considered as a separate episode of HES flare, the start date of an HES flare must be at least 14 days apart from the resolution date of the preceding HES flare.

Oral Prednisone Equivalent Daily Dose

- For each subject, oral prednisone equivalent daily dose (mg) on each day of the study will be identified from the concomitant medications page
- Partial start and end dates for concomitant medications will be handled as described in Section 13.5.2.
- Corticosteroids will be identified from the list of coded concomitant medications for the study, by merging with the GSK respiratory medication class (RMC) reference data set by component code. This reference data is created by dictionary specialists who identify a list of component terms for corticosteroids, which then undergo clinical review to ensure the correct classification is assigned.
- Only corticosteroids recorded with route = “PO” will be considered as oral corticosteroids.
- Subjects not receiving OCS therapy on any day of the study will be assigned a prednisone equivalent daily dose of 0 mg for that day.
- The corticosteroid conversion factors in the table below will be used to scale each corticosteroid dose to a prednisone equivalent dose.

Medication Name	Scaling Factor
Betamethasone	8.33
Budesonide ¹	0
Cortisone	0.2

Dexamethasone	6.67

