13.5.2. Handling of Missing and Partial Dates

Element	Reporting Detail
General	
 • Partial dates will be displayed as captured in subject listing displays.
Adverse Events and HES Flare	
 • Any partial dates for adverse events or HES flare will be raised to data management. If the full dated cannot be ascertained, the following assumptions will be made: 
 ○ If the partial date is a start date, a '01' will be used for the day and 'Jan' will be used for the month. ○ However, if this imputation results in a date prior to the first dose of open-label mepolizumab and the event could possibly have occurred during open-label mepolizumab treatment from the partial information, then the date of the first dose of mepolizumab will be assumed to be the start date. ○ The event will then be considered to start on-treatment (worst case). ○ If the partial date is a stop date, a '28/29/30/31' will be used for the day (dependent on the month and year) and 'Dec' will be used for the month. • Completely missing start or end dates will remain missing, with no imputation applied. Consequently, time to onset and duration of such events will be missing. Such events will be considered to have started after the first dose of open-label mepolizumab. • The recorded partial date will be displayed in listings.
Concomitant Medications	
 • Partial dates for any concomitant medications recorded in the CRF will be imputed using the following convention: 
 • If the partial date is a start date, a '01' will be used for the day and 'Jan' will be used for the month • If the partial date is a stop date, a '28/29/30/31' will be used for the day (dependent on the month and year) and 'Dec' will be used for the month. • The recorded partial date will be displayed in listings.

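### Daily oral corticosteroid dose inherits an earliest-start, latest-stop rule for partial dates, which lengthens dose records and leaves overlapping records undefined (minor correction)

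*SAP*

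**What the plan says.** SAP 13.4.4 (Oral Prednisone Equivalent Daily Dose) states that for each subject the "oral prednisone equivalent daily dose (mg) on each day of the study will be identified from the concomitant medications page". It continues: "Partial start and end dates for concomitant medications will be handled as described in Section 13.5.2". The mean for each 4-week period, under SAP 9.1.2.1, "will be calculated as the sum of the daily doses of OCS during each period divided by the total number of days, 28". These means feed the change from Weeks 0-4, the proportion at or below 7.5 mg (SAP 9.1.3) and the proportion with a reduction of at least 50% (SAP 9.1.4).

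The concomitant-medication row of SAP 13.5.2 opens: "Partial dates for any concomitant medications recorded in the CRF will be imputed using the following convention". A start date becomes the first of the month, with January if the month is also missing. A stop date becomes the last day of the month, with December if the month is also missing. There is no exception for OCS.

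The row above it, for adverse events and flares, has a step that the medication row lacks: "Any partial dates for adverse events or HES flare will be raised to data management". Imputation follows only if that fails.

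Neither section says what to do when two OCS records cover the same day.

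**The concern.** Widest-window imputation is a sensible default for the classification in SAP 13.2.2, where the only question is whether a drug was still in use at the first dose. A daily dose is a different quantity. Every day added to a record adds milligrams to a period mean.

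Two things follow:

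- **Carry-forward.** If OCS is stopped and the stop day is missing, the old dose runs to month end. One partial date is enough, and no assumption about combining records is needed.
- **Overlap.** If a dose change is entered as two consecutive records, a missing stop day on the old one or a missing start day on the new one can make both cover the same days. The result then depends on a programming choice that the SAP does not make.

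Protocol 5.1 lets investigators adjust background therapy from Visit 2, so the records around a dose change are the ones that carry the information these endpoints are meant to capture.

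**Working it through.** The plan states no figure to reproduce, so its rules are applied day by day to hypothetical records.

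**Inputs.** From the SAP: the imputation rule (13.5.2), the mean as the sum of daily doses over 28 (9.1.2.1), and the 7.5 mg and 50% criteria (9.1.3, 9.1.4). Assumed: the doses and change dates; Weeks 0-4 as Days 1-28 and Weeks 16-20 as Days 113-140; only the missing part of a date is imputed. Day 1 was placed on each of the 365 dates of 2018.

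**Carry-forward: 10 mg, first day off Day 116, stop day missing**

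- Truth: 3 days on drug, 3 × 10 / 28 = 1.07 mg, against 10 mg in Weeks 0-4. The reduction is 1 − 1.07/10 = 89%.
- One date worked through: with a first dose on 8 January 2018, Weeks 16-20 run from 30 April to 27 May and Day 116 is 3 May. The stop is imputed to 31 May, so all 28 days count: 28 × 10 / 28 = 10.00 mg, a reduction of 0%. Both criteria are failed.
- All 365 dates: minimum 1.07, median 6.43 (18 days counted, 18 × 10 / 28), maximum 10.00 mg. The 50% criterion is met for only 39.5% of dates.
- Placement: Day 116 is close to the worst position. With the stop spread evenly over Days 29-140 (an assumption), the 50% result flips in about 13% of cases.
- Month also missing: the stop goes to 31 December. With the same first-dose date, a course of 10 mg stopped on 12 March scores 28 × 10 / 28 = 10.00 mg in Weeks 16-20 against a truth of 0.

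**Overlap: 10 mg to 5 mg on Day 116, stop day and start day both missing**

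Truth: (3 × 10 + 25 × 5) / 28 = 155 / 28 = 5.54 mg, a change of −4.46 mg.

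| Same-day rule (none is stated) | Median over 365 dates | Range | Dates above 7.5 mg | Dates scoring an increase |
|---|---|---|---|---|
| Doses added | 11.43 mg | 5.54-15.00 | 83.6% | 60.5% |
| Higher dose used | 8.21 mg | 5.54-10.00 | 60.5% | none (maximum 10.00, equal to the starting dose) |
| Newer record governs | about 5 mg | 5.00-5.54 | none | none |

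One dosing history therefore passes or fails the 7.5 mg criterion according to an unstated rule. The percentages are shares of calendar dates in one constructed case, not shares of subjects.

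**The case against.** The strongest reply is that the trigger is uncommon and the illustration is chosen. Protocol 7.6 requires "dates of administration including start and end dates", concomitant medication is reviewed at every scheduled visit and at flare visits, monitors verify source data, and SAP 3.2 holds the final analysis until database cleaning is complete. A missing sentence in the medication row does not show that partial OCS dates go unqueried. Concomitant medications are listed by subject with recorded partial dates displayed, so affected subjects can be found. All of this stands, and it limits the size of the point.

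Placement matters as well. With the 10-to-5 mg step spread evenly over Days 29-140, both days missing and doses added, the 7.5 mg result flips in about 19% of cases and an increase is scored in about 25%. About half the cases have no error in either comparison window.

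A reader might infer that the plan will report true dose reductions as increases, or will inflate Weeks 0-4 and so exaggerate later reductions. For day-only gaps in these step-downs, both need same-day doses to be added, and no section says that they are. What the documents support is silence on the rule.

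The reply does not remove the carry-forward. The SAP links this rule to OCS explicitly and, followed as written, it gives too high a dose whenever a stop day before month end is missing.

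**Conclusion.** The point holds as a minor correction. A stated rule, applied to a quantity it does not suit, gives a wrong daily dose for any stopped OCS course whose stop day is missing and was not the last of the month. In the near-worst placement a true mean of 1.07 mg is scored at a median of 6.43 mg. Averaged over stop days, about 13% of such partial dates change the 50% result. Both figures are conditional on a partial date existing, use a hypothetical 10 mg course, and in the second case assume evenly spread stop days.

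The overlap is a gap in specification. Its effect runs from almost nothing to a reversed sign, depending on the rule chosen.

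The number of partial OCS dates is not given and is probably low. The OCS endpoints are exploratory and descriptive, with no hypothesis test, and the primary safety objective is untouched. The documents do not support a claim that the reported OCS results will be materially wrong.

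**What to change.** For OCS records, add to SAP 13.5.2 and 13.4.4:

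1. Raise partial dates to data management before imputing, as is already done for adverse events and flares.
2. For sequential records of the same OCS, let an imputed stop run no later than the day before the next record starts, and an imputed start no earlier than the day after the previous record stops. With only one of the two days missing and no gap between records, this recovers the true 5.54 mg in the step-down example.
3. Add doses only for courses recorded as truly concurrent.
4. Where dates stay unresolved (both partial, or a final stop with no following record), keep one prespecified convention, report the number of affected subjects, and show the OCS endpoints under both the earliest and the latest possible date. In the 8 January example the earliest stop, 1 May, gives 2 × 10 / 28 = 0.71 mg and the latest gives 10.00 mg, which brackets the true 1.07 mg.

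A fixed mid-month day alone would not be enough. With the 16th as last dosing day, the stopped course scores 0.00-6.43 mg, so it can under-score as well as over-score, and about 13% of first-dose dates still miss the 50% criterion.

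The cost is SAP wording, a data query, minor programming, and a check by someone that two records are sequential and not concurrent. Some approximation remains on the unknown days.

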13.6. Appendix 6: Values of Potential Clinical Importance

13.6.1. Laboratory Values

Haematology				
Laboratory Parameter	Units	Age Category	Clinical Concern Range	
			Low Flag (< x)	High Flag (>x)
Hematocrit	Ratio of 1	12+	0.201	0.599
Haemoglobin	G/L	12+	71	199
Platelet Count	GI/L	1+	31	1499
While Blood Cell Count (WBC)	GI/L	12+	1.1	

Clinical Chemistry				
Laboratory Parameter	Units	Age Category	Clinical Concern Range	
			Low Flag (< x)	High Flag (>x)
ALT	U/L	3-12		>143 (and Total Bilirubin >43)
	U/L	13+		>239 (and Total Bilirubin >43)
Calcium	mmol/L	3+	1.50	3.24
Glucose	mmol/L	1+	2.2	27.8
Phosphorus, Inorg	mmol/L	3+	0.32	
Potassium	mmol/L	3+	2.8	6.5
Sodium	mmol/L	0+	120	160
Creatine Phosphokinase	IU/L	12+		>5 x ULN

Possible Hy's Law Cases			
Laboratory Parameter	Units	Category	Clinical Concern Range
ALT, Bilirubin			ALT \geq 3xULN and Bilirubin \geq 2xULN (>35% direct)
ALT, INR			ALT \geq 3xULN and INR > 1.5

NOTES:

- ULN = Upper Limit of Normal.

13.6.2. Urinalysis

As per GSK IDSL display standards, a subject is considered to have urinalysis results of PCI if there is an increase in Protein or an increase in Occult Blood results during the study, or if microscopy is performed.

13.7. Appendix 7: Abbreviations & Trade Marks

13.7.1. Abbreviations

Abbreviation	Description
ADaM	Analysis Data Model
AE	Adverse Event
AIC	Akaike's Information Criteria
A&R	Analysis and Reporting
CDISC	Clinical Data Interchange Standards Consortium
CI	Confidence Interval
CPMS	Clinical Pharmacology Modelling & Simulation
CS	Clinical Statistics
CSR	Clinical Study Report
CTR	Clinical Trial Register
CV _b / CV _w	Coefficient of Variation (Between) / Coefficient of Variation (Within)
DBF	Database Freeze
DBR	Database Release
DOB	Date of Birth
DP	Decimal Places
eCRF	Electronic Case Record Form
EMA	European Medicines Agency
FDA	Food and Drug Administration
FDAAA	Food and Drug Administration Clinical Results Disclosure Requirements
GSK	GlaxoSmithKline
IA	Interim Analysis
ICH	International Conference on Harmonization
IDMC	Independent Data Monitoring Committee
IDSL	Integrated Data Standards Library
IMMS	International Modules Management System
IP	Investigational Product
ITT	Intent-To-Treat
MMRM	Mixed Model Repeated Measures
PCI	Potential Clinical Importance
PD	Pharmacodynamic
PDMP	Protocol Deviation Management Plan
PK	Pharmacokinetic
PP	Per Protocol
PopPK	Population PK
QC	Quality Control
QTcF	Frederica's QT Interval Corrected for Heart Rate
QTcB	Bazett's QT Interval Corrected for Heart Rate
RAP	Reporting & Analysis Plan
RAMOS	Randomization & Medication Ordering System
SAC	Statistical Analysis Complete
SDSP	Study Data Standardization Plan

Abbreviation	Description
SDTM	Study Data Tabulation Model
SoA	Schedule of Activities
SoC	Standard of Care
SOP	Standard Operation Procedure
TA	Therapeutic Area
TFL	Tables, Figures & Listings

13.7.2. Trademarks

Trademarks of the GlaxoSmithKline Group of Companies
NONE

Trademarks not owned by the GlaxoSmithKline Group of Companies
SAS

13.8. Appendix 8: List of Data Displays

13.8.1. Data Display Numbering

The following numbering will be applied for RAP generated displays:

Section	Tables	Figures
Study Population	1.1 to 1.n	1.1 to 1.n
Efficacy	2.1 to 2.n	2.1 to 2.n
Safety	3.1 to 3.n	3.1 to 3.n
Pharmacokinetic	4.1 to 4.n	4.1 to 4.n
Pharmacodynamic and / or Biomarker	6.1 to 6.n	6.1 to 6.n
Section	Listings	
ICH Listings	1 to x	

13.8.2. Mock Example Shell Referencing

Non IDSL specifications will be referenced as indicated and if required example mock-up displays provided in [Appendix 9](#): Example Mock Shells for Data Displays.

Section	Figure	Table	Listing
Study Population	POP_Fn	POP_Tn	POP_Ln
Efficacy	EFF_Fn	EFF_Tn	EFF_Ln
Safety	SAFE_Fn	SAFE_Tn	SAFE_Ln
Pharmacokinetic	PK_Fn	PK_Tn	PK_Ln
Pharmacodynamic and / or Biomarker	PD_Fn	PD_Tn	PD_Ln

NOTES:

- Non-Standard displays are indicated in the 'IDSL / Example Shell' or 'Programming Notes' column as '[Non-Standard] + Reference.'

13.8.3. Deliverables

Deliverable	Description
SAC	Final Statistical Analysis Complete

13.8.4. Study Population Tables

Study Population Tables					
No.	Population	IDSL / Example Shell	Title	Programming Notes	Deliverable
Subject Disposition					
1.1.	Safety	ES1	Summary of Subject Disposition	Include Completed, Withdrawn and subsets of completed/withdrawn as follows:- Completed, Completed Week 20, Completed Week 20 and Follow-up Withdrawn, Withdrawn prior to Week 20, Completed Week 20 and withdrawn prior to Follow up	SAC
1.2.	Safety	SD1	Summary of Treatment Status and Reasons for Discontinuation of Study Treatment		SAC
1.3.	Safety	POP_T1	Summary of Subject Accountability During 20-Week Treatment Period		SAC
1.4.	Screened	ES6	Summary of Screening Status and Reasons for Screen Failure		SAC
1.5.	Enrolled	NS1	Summary of Number of Subjects by Country and Site ID		SAC
Protocol Deviation					
1.6.	Safety	DV1	Summary of Important Protocol Deviations		SAC
Population Analysed					
1.7.	Safety	SP1	Summary of Study Populations		SAC
Demographic and Baseline Characteristics					
1.8.	Safety	DM1	Summary of Demographic Characteristics		SAC
1.9.	Enrolled	DM11	Summary of Age Ranges		SAC

Study Population Tables					
No.	Population	IDSL / Example Shell	Title	Programming Notes	Deliverable
1.10.	Safety	DM5	Summary of Race and Racial Combinations		SAC
Prior and Concomitant Medications/Conditions					
1.11.	Safety	CM1	Summary of Concomitant Medications		SAC
Exposure and Treatment Compliance					
1.12.	Safety	POP_T2	Summary of Exposure (Therapeutic Coverage) to Study Treatment		SAC
1.13.	Safety	POP_T3	Summary of Number of Treatments Administered		SAC

13.8.5. Safety Tables

No.	Population	IDSL / Example Shell	Title	Programming Notes	Deliverable
Adverse Events					
2.1.	Safety	AE1	Summary of All On-Treatment Adverse Events by System Organ Class and Preferred Term		SAC
2.2.	Safety	AE1	Summary of All Post-Treatment Adverse Events by System Organ Class and Preferred Term		SAC
2.3.	Safety	AE3	Summary of Common ($\geq 3\%$ Incidence) On-Treatment Adverse Events by Overall Frequency		SAC
2.4.	Safety	AE15	Summary of Common ($\geq 3\%$ Incidence) On-Treatment Non-Serious Adverse Events by System Organ Class and Preferred Term (Number of Subjects and Occurrences)		SAC
2.5.	Safety	AE5A	Summary of All On-Treatment Adverse Events by Maximum Intensity by System Organ Class and Preferred Term		SAC
2.6.	Safety	AE1	Summary of All Drug-Related Adverse Events by System Organ Class and Preferred Term		SAC
2.7.	Safety	AE5A	Summary of All Drug-Related Adverse Events by Maximum Intensity by System Organ Class and Preferred Term		SAC
2.8.	Safety	AE1	Summary of Non-Serious Drug-Related Adverse Events by System Organ Class and Preferred Term		SAC
2.9.	Safety	AE1	Summary of On-Treatment Adverse Events by Highest Post-Baseline Binding Antibody Result	Add in row with n in each binding antibody result category.	SAC
2.10.	Safety	AE3	Summary of All Adverse Events Leading to Permanent Discontinuation from Study Treatment by Overall Frequency		SAC

CONFIDENTIAL

205203

No.	Population	IDSL / Example Shell	Title	Programming Notes	Deliverable
Adverse Events					
2.11.	Safety	AE3	Summary of All Adverse Events Leading to Withdrawal from the Study by Overall Frequency		SAC
2.12.	Safety	AE1	Summary of Adverse Events Reported on the Day of Dosing by System Organ Class and Preferred Term		SAC
2.13.	Safety	AE7	Listing of Subject Numbers for Individual On-Treatment Adverse Events		SAC
2.14.	Safety	AE7	Listing of Subject Numbers for Individual Post-Treatment Adverse Events		SAC
2.15.	Safety	AE2	Listing of Relationship of Adverse Event, System Organ Classes, Preferred Terms and Verbatim Text		SAC
Adverse Event Overview					
2.16.	Safety	SAFE_T1	Adverse Event Overview		SAC
Serious Adverse Events					
2.17.	Safety	AE3	Summary of Fatal Serious Adverse Events by Overall Frequency		SAC
2.18.	Safety	AE3	Summary of Drug-Related Fatal Serious Adverse Events by Overall Frequency		SAC
2.19.	Safety	AE3	Summary of Non-Fatal Serious Adverse Events by Overall Frequency		SAC
2.20.	Safety	AE3	Summary of All Serious Adverse Events by Overall Frequency		SAC
2.21.	Safety	AE1	Summary of All On-Treatment Serious Adverse Events by System Organ Class and Preferred Term		SAC

CONFIDENTIAL

205203

No.	Population	IDSL / Example Shell	Title	Programming Notes	Deliverable
2.22.	Safety	AE1	Summary of All Post-Treatment Serious Adverse Events by System Organ Class and Preferred Term		SAC
2.23.	Safety	AE1	Summary of All Pre-Treatment Serious Adverse Events by System Organ Class and Preferred Term		SAC
2.24.	Safety	AE16	Summary of All Serious Adverse Events by System Organ Class and Preferred Term (Number of Subjects and Occurrences)		SAC
2.25.	Safety	AE1	Summary of All Drug-Related Serious Adverse Events by System Organ Class and Preferred Term		SAC
Adverse Events of Special Interest					
2.26.	Safety	AE1	Summary of On-Treatment Adverse Events Reported by the Investigator as Systemic Reactions Meeting the Criteria for Anaphylaxis		SAC
2.27.	Safety	SAFE_T2	Summary Profile of On-Treatment Adverse Events Reported by the Investigator as Systemic Reactions Meeting the Criteria for Anaphylaxis		SAC
2.28.	Safety	AE1	Summary of On-Treatment Adverse Events Reported by the Investigator as Systemic Reactions - Allergic (Type I Hypersensitivity) and Other Systemic		SAC
2.29.	Safety	SAFE_T2	Summary Profile of On-Treatment Adverse Events by the Investigator as Systemic Reactions - Allergic (Type I Hypersensitivity) and Other Systemic		SAC
2.30.	Safety	AE1	Summary of On-Treatment Adverse Events Reported by the Investigator as Systemic Reactions - Allergic (Type I Hypersensitivity)		SAC

CONFIDENTIAL

205203

No.	Population	IDSL / Example Shell	Title	Programming Notes	Deliverable
2.31.	Safety	SAFE_T2	Summary Profile of On-Treatment Adverse Events Reported by the Investigator as Systemic Reactions - Allergic (Type I Hypersensitivity)		SAC
2.32.	Safety	AE1	Summary of On-Treatment Adverse Events Reported by the Investigator as Systemic Reactions – Other Systemic		SAC
2.33.	Safety	SAFE_T2	Summary Profile of On-Treatment Adverse Events Reported by the Investigator as Systemic Reactions - Other Systemic		SAC
2.34.	Safety	AE1	Summary of On-Treatment Adverse Events Reported by the Investigator as Local Injection Site Reactions		SAC
2.35.	Safety	SAFE_T2	Summary Profile of On-Treatment Adverse Events Reported by the Investigator as Local Injection Site Reactions		SAC
2.36.	Safety	AE1	Summary of On-Treatment Adverse Events Categorised as Serious Cardiac, Vascular and Thromboembolic Events		SAC
2.37.	Safety	SAFE_T2	Summary Profile of On-Treatment Adverse Events Categorised as Serious Cardiac, Vascular and Thromboembolic Events		SAC
2.38.	Safety	AE1	Summary of On-Treatment Adverse Events Categorised as Serious Ischemic Events		SAC
2.39.	Safety	SAFE_T2	Summary Profile of On-Treatment Adverse Events Categorised as Serious Ischemic Events		SAC
2.40.	Safety	AE1	Summary of On-Treatment Adverse Events Categorised as Malignancies		SAC
2.41.	Safety	SAFE_T2	Summary Profile of On-Treatment Adverse Events Categorised as Malignancies		SAC

No.	Population	IDSL / Example Shell	Title	Programming Notes	Deliverable
2.42.	Safety	AE1	Summary of On-Treatment Adverse Events Categorised as Potential Opportunistic Infections		SAC
2.43.	Safety	SAFE_T2	Summary Profile of On-Treatment Adverse Events Categorised as Potential Opportunistic Infections		SAC
Laboratory – Haematology					
2.44.	Safety	LB1	Summary of Haematology Changes from Baseline by Visit	Include baseline values	SAC
2.45.	Safety	LB3	Summary of Haematology Shifts from Baseline Relative to Normal Range by Visit	Include worst case post-baseline. If there are unscheduled assessments add footnote: "Note: Worst case post baseline Includes scheduled and unscheduled assessments."	SAC
2.46.	Safety	LB3	Summary of Haematology Shifts from Baseline Relative to PCI Criteria by Visit	Include worst case post-baseline. If there are unscheduled assessments add footnote: "Note: Worst case post baseline Includes scheduled and unscheduled assessments."	SAC
Laboratory – Clinical Chemistry					
2.47.	Safety	LB1	Summary of Clinical Chemistry Changes from Baseline by Visit	Include baseline values	SAC
2.48.	Safety	LB3	Summary of Clinical Chemistry Shifts from Baseline Relative to Normal Range by Visit	Include worst case post-baseline. If there are unscheduled assessments add footnote: "Note: Worst case post baseline Includes scheduled and unscheduled assessments."	SAC

No.	Population	IDSL / Example Shell	Title	Programming Notes	Deliverable
2.49.	Safety	LB3	Summary of Clinical Chemistry Shifts from Baseline Relative to PCI Criteria by Visit	Include worst case post-baseline. If there are unscheduled assessments add footnote: "Note: Worst case post baseline Includes scheduled and unscheduled assessments."	SAC
Laboratory – Urinalysis					
2.50.	Safety	UR1	Summary of Worst Case Urinalysis Results Post-Baseline Relative to Baseline		SAC
Laboratory: Hepatobiliary (Liver)					
2.51.	Safety	LIVER1	Summary of Liver Monitoring/Stopping Event Reporting		SAC
2.52.	Safety	LIVER10	Summary of Hepatobiliary Laboratory Abnormalities		SAC
ECG					
2.53.	Safety	EG1	Summary of ECG Findings by Visit	Include worst case post-baseline. If there are unscheduled assessments add footnote: "Note: Worst case post baseline Includes scheduled and unscheduled assessments."	SAC
2.54.	Safety	EG2	Summary of Change from Baseline in ECG Values by Visit	Include baseline values	SAC
2.55.	Safety	EG10	Summary of Maximum QTc Values Post-Baseline Relative to Baseline by Category	QTc(B) and QTc(F) If there are unscheduled assessments add footnote: "Note: Includes scheduled and unscheduled assessments."	SAC

No.	Population	IDSL / Example Shell	Title	Programming Notes	Deliverable
2.56.	Safety	EG11	Summary of Maximum Increase in QTc Values Post-Baseline Relative to Baseline by Category	QTc(B) and QTc(F) If there are unscheduled assessments add footnote: "Note: Includes scheduled and unscheduled assessments."	SAC
Vital Signs					
2.57.	Safety	VS1	Summary of Vital Signs by Visit		SAC
2.58.	Safety	VS1	Summary of Change from Baseline in Vital Signs by Visit	Include baseline values	SAC
Immunogenicity					
2.59.	Safety	SAFE_T3	Summary of Binding Antibody by Visit	Include highest post baseline result.	SAC
2.60.	Safety	SAFE_T3	Summary of Binding Antibody By Visit – Subjects Without Positive Result Prior to Dosing	Post-Week 0 visits only, plus highest post baseline result.	SAC
2.61.	Safety	SAFE_T4	Summary of Neutralising Antibody by Visit	Include highest post baseline result.	SAC

